### 5.6 Acceptable Concomitant Medications

All treatments that the investigator considers necessary for a subject’s welfare may be administered at the discretion of the investigator in keeping with the community standards of medical care. All concomitant medication will be recorded on the case report form (CRF) including all prescription, over-the-counter (OTC), herbal supplements, and IV medications and fluids. If changes occur during the trial period, documentation of drug dosage, frequency, route, and date may also be included on the CRF.

All concomitant medications received within 28 days before the first dose of trial treatment and 30 days after the last dose of trial treatment should be recorded. Concomitant medications administered after 30 days after the last dose of trial treatment should be recorded for SAEs and ECIs as defined in Section 7.4.

### 5.7 Prohibited Concomitant Medication

Subjects are prohibited from receiving the following therapies during the Screening and Treatment Phase (including retreatment for post-complete response relapse) of this trial:

- Antineoplastic systemic chemotherapy or biological therapy
- Immunotherapy not specified in this protocol
- Chemotherapy not specified in this protocol
- Investigational agents other than pembrolizumab
- Radiation therapy
  - Note: Radiation therapy to a symptomatic lesion may be allowed at the investigator’s discretion. If radiation is given to a solitary lesion at the investigator's discretion, then the patient is considered to have progressive disease, but may continue on treatment if patient is clinically stable.
- Live vaccines within 30 days prior to the first dose of trial treatment and while participating in the trial. Examples of live vaccines include, but are not limited to, the following: intranasal influenza vaccines (e.g., Flu-Mist®), measles, mumps, rubella, varicella/zoster, yellow fever, rabies, BCG, and typhoid vaccine.

- Systemic glucocorticoids for any purpose other than to treat edema related to the meningioma or supportive post-operative management or to modulate symptoms from an event of clinical interest of suspected immunologic etiology. Intranasal, inhaled or topical corticosteroids (<5% of body surface area) for the treatment of mild/moderate asthma, allergies or dermatitis are permitted. The use of physiologic doses of corticosteroids may be approved after consultation with the Overall PI. Physiologic replacement of glucocorticoids as maintenance therapy for adrenal insufficiency are permitted. Standard doses of hydrocortisone for maintenance therapy are 10–20 mg/m^2/day divided 2–4 times per day. For a subject with a body surface area (BSA) of 1.73 m^2, this translates to a total dose of 34.6 mg of hydrocortisone per day. The equivalent dose of dexamethasone is 1.2 mg per day. Some subjects may additionally receive mineralocorticoid- replacement maintenance therapy with fludrocortisone. The maintenance dose of fludrocortisone for this indication is 0.05–0.1 mg/day. Antihistamines and other non-steroidal anti-allergy medications are also permitted.

Subjects who, in the assessment by the investigator, require the use of any of the aforementioned treatments for clinical management should be removed from the trial. Subjects may receive other medications that the investigator deems to be medically necessary.

The Exclusion Criteria describes other medications which are prohibited in this trial.

There are no prohibited therapies during the Post-Treatment Follow-up Phase.

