## 3.0 PARTICIPANT SELECTION

### 3.1 Eligibility Criteria

#### 3.1.1 Documentation Of Disease

**Histologic Documentation:** Histologically proven recurrent or residual intracranial or metastatic meningioma or meningioma with extracranial spread

**Progressive OR residual disease**, as defined by the following:

**Progressive disease**, as defined as an increase in size of a measurable meningioma lesion on imaging by greater than 25% (bidirectional area). The change must occur between scans separated by no more than 24 months.

**Residual measurable disease:** For Grade II or III meningioma, residual measurable disease immediately after surgery without requirement for progression. Residual measurable disease will be defined by measurable lesions with clearly defined margins by MRI scans, with a minimum diameter of 10mm in one dimension.

**Post radiation patients:** Patients with measurable and progressive meningioma who have received radiation are potentially eligible, but need to show evidence of progressive disease in the radiated field after completion of radiation.  $\geq 24$  weeks must have elapsed from completion of radiation to registration. Patients that have progressive disease outside of the radiation field do not need to wait 24 weeks from completion of radiation.

**3.1.2 Measurable Disease:** Measurable disease is defined by a main lesion measurable on MRI or CT images (MRI preferred) with clearly defined margins and  $\geq 10$  mm in one dimension. Multifocal disease is allowed as long as one lesion meets criteria for measurable disease and progressive disease. For measurable disease, refer to Section 11.0

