**3.1.3 Prior Treatment**

- Prior medical therapy is allowed but not required.
- Meningioma that have resulted from prior radiation therapy are allowed.
- No limit on number of prior therapies.
- No chemotherapy, other investigational agents within 14 days of study treatment.
- No other concurrent investigational agents or other meningioma-directed therapy (chemotherapy, radiation) while on study.
- For patients treated with external beam radiation, interstitial brachytherapy or radiosurgery, an interval  $\geq 24$  weeks must have elapsed from completion of XRT to registration.
- Stable dose of dexamethasone 2mg or less for at least 7 days prior to initiation of treatment.
- Recovered to CTCAE grade 1 or less toxicity from other agents with exception of alopecia and fatigue.
- No craniotomy within 21 days of registration.
- Grade I meningiomas will be allowed as long as they meet criteria for progression as defined by 3.1.1.

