Scheduling Window (Days):	-14 to 0		± 3	± 3	± 3	± 3	± 3	± 3	± 3	At time of Discon	30 days post discon	Every 6 weeks	Every 3 months
Research Blood x	X	X		X		X		X		X			

aAll screening procedures to be performed within 14 days of start of study treatment, except scans which can be obtained within 21 days of starting study treatment, and informed consent may occur up to 28 days prior to start of study treatment

bC1D1 and Day 1 of subsequent cycles: For C1D1 screening assessments may serve as day 1 assessments if performed within 7 days before start of study treatment, except serum pregnancy (within 72 hours of drug) and except in the event that there are any indications that the participant's condition is deteriorating for which laboratory evaluations should be repeated within 48 hours prior to initiation. C1D1 labs must meet eligibility criteria. For all subsequent cycles, required assessments should be performed within 3 days of scheduled cycle day 1.

cStudy drug therapy administration windows include  $\pm 3$  days for each agent.

dEnd of Tx: End of treatment assessments to be performed within 7 days after last day drug administration or within 7 days after decision to end treatment. Assessments may continue for ongoing reportable adverse events.

e30-Day Post Drug: A contact/visit is to be performed at 30 days (+/-5 days) after the last study drug is given. This may be performed via documented phone conversation with a study nurse or clinician or a clinic visit. All participants will be followed until resolution or stabilization of any serious or reportable adverse events occurring during treatment or starting within 30 days of last study drug.

fActive Follow Up: In participants who discontinue study treatment without documented disease progression, every effort should be made to continue monitoring their disease status by radiologic imaging every 6 weeks (+/- 7 days) until (1) the start of new anti-cancer treatment, (2) documented disease progression, or (3) death whichever occurs first.

gLong Term Follow Up: participants will be followed every 3 months (+/- 1 month) via contact or medical record review until death for post-treatment therapies, reason for stopping those therapies and survival.

hInformed Consent: Informed Consent may be obtained within 28 days of start of study treatment

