tTSH will be performed at baseline, week 1, beginning of cycle 2 and then every 2 cycles. TSH results do not need to be back prior to dosing

uBrain MRI will be performed every 2 cycles. In the rare circumstance where patients have extracranial metastases, chest/abd/pelvis CT will also be obtained every 2 cycles. If pembrolizumab is held or interrupted, the scan schedule should be maintained at every 2 cycles.

vAs per section 5.12, completed 24 months of uninterrupted treatment with pembrolizumab or 35 administrations of study medication, whichever is later

wTissue collected as part of clinical care (e.g. from prior biopsy, craniotomy) will be collected. Tissue needs to be submitted within 30 days after patient enrollment. See Section 9 for specimen collection requirements

xBlood will be collected at screening every 2 cycles (two 10 mL EDTA/lavender top tube) and at the end of treatment

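### Section 5.7 counts on-study radiation as progression only for a solitary lesion, and the PFS6 scoring rules omit radiation, so read literally an irradiated patient with multifocal disease could be scored a success

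*Combined protocol and SAP*

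**What the plan says.** Section 5.7 lists radiation among the prohibited therapies and then adds a note. The permission reads "Radiation therapy to a symptomatic lesion may be allowed"; the choice is left to the investigator. The consequence follows in the next sentence: "If radiation is given to a solitary lesion at the investigator's discretion, then the patient is considered to have progressive disease". That sentence goes on to let such a patient stay on drug: "but may continue on treatment if patient is clinically stable". The note gives no date for that progression. The same section ends by saying that subjects who "require the use of any of the aforementioned treatments for clinical management should be removed from the trial", and it does not name the note as an exception. Section 3.1.3 states a general bar: "No other concurrent investigational agents or other meningioma-directed therapy (chemotherapy, radiation) while on study".

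Section 3.1.2 makes patients with more than one lesion eligible: "Multifocal disease is allowed as long as one lesion meets criteria for measurable disease and progressive disease".

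Section 13.2 defines PFS6 as freedom from progression and death for six months from the first day of treatment. It refers to Section 11 for the criteria and does not cite Section 5.7. In Section 11, radiation appears neither in the intracranial progression list (11.3.1.1), nor in the rules for continuing past initial progression and for enhancement-only assessment (11.3.3), nor in the extracranial rule (11.4.4.1), nor in the PFS definition (11.4.6). Section 11.3.4 has the central reader apply the Section 11 criteria.

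Section 13.6 calls the drug worthy of further study if at least 10 of 24 evaluable patients reach six months progression-free. The null rate is 26%, the target 52%, the one-sided level 0.1, and the stated power at least 88%.

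**The concern.** The permission and the consequence use different words. Permission covers a symptomatic lesion, while progression is declared for a solitary one. Where multifocal disease is eligible, these need not be the same patients.

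Radiation can control the lesion being measured. In a single-arm trial, a patient who is irradiated, has no progression recorded and stays on drug would have that control counted as benefit of pembrolizumab in the primary endpoint. Best response under Section 11.3.1.2 runs until progression, so later scans of the irradiated lesion could also count toward response. An error of this kind can only push the decision toward a positive result.

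**Working it through.** **Step 1: the two readings, side by side.**

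| | Solitary = the patient's only lesion | Solitary = the one lesion irradiated |
|---|---|---|
| One-lesion patient, irradiated | Progression under 5.7 | Progression under 5.7 |
| Multifocal patient, one lesion irradiated | Not progression under 5.7; Section 11 silent | Progression under 5.7 |
| Event date | Not given | Not given |
| Link to Section 11 and 13.2 | Missing | Missing |

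The readings differ only in the second row. Scoring from Section 11 alone would give the same gap for any irradiated patient.

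**Step 2: who is exposed.** For patients who leave treatment without progression, Study Calendar footnote f ends status imaging at, among other events, "the start of new anti-cancer treatment". The exposed patient is therefore one who stays on treatment under the note and keeps the regular schedule in footnote u: "Brain MRI will be performed every 2 cycles". That patient must also meet none of the other progression criteria in 11.3.1.1, which include clear clinical worsening.

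**Step 3: reproduce the design.** Inputs from Section 13.6: n = 24, cut-off 10, null 0.26, target 0.52. X is the number of successes, exact binomial.

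- Null pass probability: P(X ≥ 10 | 24, 0.26) = 0.0692.
- Power: P(X ≥ 10 | 24, 0.52) = 0.8884, which agrees with the stated figure of at least 88%.
- A cut-off of 9 would give P(X ≥ 9 | 24, 0.26) = 0.1467, so 10 is the smallest cut-off that keeps the 0.1 level.

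**Step 4: sensitivity to one patient.** Assume that one of the 24 is irradiated and scored a success whatever the true status. This count is an assumption; the documents give none. The other 23 must then supply at least 9 successes:

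- P(X ≥ 9 | 23, 0.26) = 0.1177.
- Increase: 0.1177 − 0.0692 = 0.0485.
- Check: the decision changes only if exactly 9 of the other 23 succeed (probability 0.0655) and the irradiated patient would otherwise have failed (probability 1 − 0.26 = 0.74). The product is 0.74 × 0.0655 = 0.0485.

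Under the second reading the patient is a failure, and this inflation does not arise.

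**Step 5: the missing date.** PFS6 is a yes/no endpoint. The date changes a patient's status only if the possible dates for the event, such as the decision to irradiate and its delivery, fall on different sides of month 6.

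**The case against.** The strongest reply is that Section 5.7 already settles the matter. Its two sentences are consecutive and both turn on the investigator's discretion, so the solitary lesion is naturally the symptomatic one just permitted. The other reading makes radiation a failure for a patient with one lesion but not for a patient with several, and nothing in the protocol suggests that intent. An express progression rule in 5.7 is not cancelled because 13.2 refers to Section 11. Nor does continued treatment imply success, since Section 5.12 also allows a clinically stable patient with confirmed radiographic progression to continue.

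Much of this stands. The second reading is reasonable, and clear clinical worsening would catch some symptomatic patients. The general bar in 3.1.3 and the removal sentence in 5.7 also narrow the case. The response harm is limited too: Section 13.7 counts CR, PR or SD, so a patient with stable disease before radiation may already count. But none of this removes the mismatch in wording or supplies the date or the link to the scoring criteria.

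Two stronger conclusions are tempting and not supported. A reader might infer that the trial's false-positive rate is 11.8%; that figure is conditional on one such patient, whom the documents do not quantify. A reader might also infer that the fix costs power. Forcing one patient to fail while holding the other 23 at 52% gives P(X ≥ 10 | 23, 0.52) = 0.8477. That is no loss against the plan if the 52% target already counts irradiated patients as failures.

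**Conclusion.** The concern holds in limited form. On a literal reading, a patient with multifocal disease who has one symptomatic lesion irradiated, meets no other progression criterion and stays on pembrolizumab could be scored a PFS6 success. On the other reading that patient is already a failure, and what remains is an undated event that Section 11 does not mention; for PFS6 this matters mainly near month 6.

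The likely number of such patients is small and cannot be read from the documents. The sensitivity figure, 6.9% rising to 11.8% for one patient fixed as a success, shows only that the 10-of-24 rule cannot absorb one such misclassification and stay within its 10% level. The point is worth correcting because the change is small and should be settled before outcomes are scored.

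**What to change.** In Section 5.7, replace the reference to a solitary lesion with *any meningioma lesion*. In Section 13.2, add one sentence that also governs Section 11, for example: *On-study radiation to meningioma counts as progression for PFS6, dated at the start of radiation or at earlier documented progression; later scans do not count toward response.*

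Cross-references in 3.1.3 and in the removal sentence of 5.7 would be tidy but are optional, since the specific note can reasonably be read as qualifying the general rules.

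The cost is protocol wording only, with no new data. The observed PFS6 may be slightly less favourable. Stating that the 52% target treats irradiated patients as failures keeps the design at its planned 6.9% null pass probability and 88.8% power.

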### **5.8 Diet**

Subjects should maintain a normal diet unless modifications are required to manage an adverse event such as diarrhea, nausea or vomiting.

### **5.9 Contraception**

Pembrolizumab may have adverse effects on a fetus in utero. Furthermore, it is not known if pembrolizumab has transient adverse effects on the composition of sperm. Non-pregnant, non-breast-feeding women may be enrolled if they are willing to use 2 methods of birth control or are considered highly unlikely to conceive. Highly unlikely to conceive is defined as 1) surgically sterilized, or 2) postmenopausal (a woman who is  $\geq 45$  years of age and has not had menses for greater than 1 year will be considered postmenopausal), or 3) not heterosexually active for the duration of the study. The two birth control methods can be either two barrier methods or a barrier method plus a hormonal method to prevent pregnancy. Subjects should start using birth control from study Visit 1 throughout the study period up to 120 days after the last dose of study therapy.

The following are considered adequate barrier methods of contraception: diaphragm, condom (by the partner), copper intrauterine device, sponge, or spermicide. Appropriate hormonal contraceptives will include any registered and marketed contraceptive agent that contains an estrogen and/or a progestational agent (including oral, subcutaneous, intrauterine, or intramuscular agents).

Subjects should be informed that taking the study medication may involve unknown risks to the fetus (unborn baby) if pregnancy were to occur during the study. In order to participate in the study they must adhere to the contraception requirement (described above) for the duration of the study and during the follow-up period defined in section 7.2-Reporting of Pregnancy and Lactation to the Overall PI and to Merck. If there is any question that a subject will not reliably comply with the requirements for contraception, that subject should not be entered into the study.

### **5.10 Use in Pregnancy**

If a subject inadvertently becomes pregnant while on treatment with pembrolizumab, the subject will immediately be removed from the study. The site will contact the subject at least monthly and document the subject's status until the pregnancy has been completed or terminated. The outcome of the pregnancy will be reported to the Overall PI and to Merck without delay and within 24 hours to the Overall PI and within 2 working days to Merck if the outcome is a serious adverse experience (e.g., death, abortion, congenital anomaly, or other disabling or life-threatening complication to the mother or newborn).

The study investigator will make every effort to obtain permission to follow the outcome of the pregnancy and report the condition of the fetus or newborn to the Overall PI. If a male subject impregnates his female partner the study personnel at the site must be informed immediately and the pregnancy reported to the Overall PI and to Merck and followed as described above and in Section 7.2.

### **5.11 Use in Nursing Women**

It is unknown whether pembrolizumab is excreted in human milk. Since many drugs are excreted in human milk, and because of the potential for serious adverse reactions in the nursing infant, subjects who are breast-feeding are not eligible for enrollment.

### **5.12 Criteria for Taking a Participant Off Protocol Therapy**

Duration of therapy will depend on individual response, evidence of disease progression and tolerance. In the absence of treatment delays due to adverse event(s), treatment may continue until one of the following criteria applies:

- Confirmed radiographic disease progression

*Note:* For unconfirmed radiographic disease progression, please see Section 11.3.3

*Note:* A subject may be granted an exception to continue on treatment with confirmed radiographic progression if clinically stable or clinically improved.

- Intercurrent illness that prevents further administration of treatment
- Unacceptable adverse event(s)

- Participant demonstrates an inability or unwillingness to comply with trial regimen and/or documentation requirements
- Participant decides to withdraw from the protocol therapy
- General or specific changes in the participant's condition render the participant unacceptable for further treatment in the judgment of the treating investigator
- The subject has a confirmed positive serum pregnancy test
- Subject is lost to follow-up
- Completed 24 months of uninterrupted treatment with pembrolizumab or 35 administrations of study medication, whichever is later.

Participants will be removed from the protocol therapy when any of these criteria apply. The reason for removal from protocol therapy, and the date the participant was removed, must be documented in the case report form (CRF). Alternative care options will be discussed with the participant.

An ODQ Treatment Ended/Off Study Form will be filled out when a participant is removed from protocol therapy. This form can be found on the DF/HCC website at <http://www.dfhcc.harvard.edu/research/clinical-research-support/document-library-forms-sops-etc/>.

In the event of unusual or life-threatening complications, treating investigators must immediately notify the Overall PI, [name] at [contact].

### **5.13 Duration of Follow Up**

After the end of treatment, each subject will be followed for 30 days for adverse event monitoring (serious adverse events will be collected for 90 days after the end of treatment as described in Section 7.3). Subjects who discontinue for reasons other than progressive disease will have post-treatment follow-up for disease status until disease progression, initiating a non-study cancer treatment, withdrawing consent or becoming lost to follow-up. After documented disease progression each subject will be followed by telephone for overall survival until death, or withdrawal of consent, whichever occurs first.

### **5.14 Criteria for Taking a Participant Off Study**

Participants will be removed from study when any of the following criteria apply:

- Lost to follow-up
- Withdrawal of consent for data submission
- Death

The reason for taking a participant off study, and the date the participant was removed, must be documented in the case report form (CRF).

For Decentralized Subject Registrations, the research team updates the relevant Off Treatment/Off Study information in OnCore.

